5.6.2. Benefit Assessment

Data from earlier studies [Haldar, 2009; Nair, 2009; Pavord, 2012] attest to the clinical utility of mepolizumab in the treatment of severe eosinophilic asthma, as do the data from recently completed Phase III studies MEA115575 and MEA115588 [Bel, 2014; Ortega, 2014].

In this study, benefit considerations for a subject may include:

- Continuation to receive active drug during study conduct that may have clinical benefit, even for subjects randomized to placebo who may undergo switch to open-label mepolizumab after experiencing one clinically significant asthma exacerbation
- Contributing to the process of developing new therapies in an area of unmet need, and providing insight into the need for continuous therapy in order to receive clinical benefit
- Medical evaluations/assessments associated with study procedures

5.6.3. Overall Benefit:Risk Conclusion

Current data from mepolizumab preclinical and clinical development indicate the ability of mepolizumab to inhibit IL-5 leading to consistent reduction in blood eosinophils, with demonstration of clinical benefit in the treatment of conditions associated with eosinophilic inflammation, such as asthma. Data from the Phase III asthma programme with mepolizumab demonstrates, compared to placebo, a reduction in asthma exacerbations, improvements in asthma control and quality of life (as measured by the ACQ and SGRQ, respectively), improvements in lung function and a reduction in steroid use in those subjects on chronic OCS treatment. To date, the safety profile of mepolizumab compared to placebo has been favorable and AEs reported commonly are non-serious and manageable with minimal supportive care. Furthermore, evaluation of the post-treatment adverse event data from the severe asthma clinical program does not support an exaggerated return of symptoms after cessation of treatment.

Considering the measures taken to minimize risk to a subject participating in this study, the potential risks identified are justified by the anticipated benefits that may be afforded to a subject with severe asthma. Therefore, the Sponsor considers that investigation of the effect of cessation versus continuation of long-term mepolizumab treatment in patients with severe eosinophilic asthma is justified in study 201810 with a positive benefit/risk ratio.

6. SELECTION OF STUDY POPULATION, IP DISCONTINUATION AND WITHDRAWAL CRITERIA

Specific information regarding warnings, precautions, contraindications, adverse events, and other pertinent information on the GSK investigational product or other study treatment that may impact subject eligibility is provided in the IB/IB supplement(s).

Deviations from inclusion and exclusion criteria are not allowed because they can potentially jeopardize the scientific integrity of the study, regulatory acceptability or subject safety. Therefore, adherence to the criteria as specified in the protocol is essential.

6.1. Inclusion Criteria

A subject will be eligible for inclusion in this study only if ALL of the following criteria apply:

1. **Informed Consent:** Prior to commencing any study related activities, subjects must be able and willing to provide written informed consent, and an assent for subjects under 18 years of age, at Visit 0 (or Visit 1 if these Visits are conducted on the same day).
2. **Continuous Mepolizumab Treatment during MEA115666 or 201312:** Participation through the Follow Up/Exit Visit or Early Withdrawal Visit and documented evidence of treatment with mepolizumab with no treatment gaps of more than 12 weeks (84 days) between any two doses within MEA115666 or 201312. (A treatment gap of more than 12 weeks [84 days] cannot occur between the end of MEA115666 or 201312 and Visit 1).
3. **Current Anti-Asthma Therapy:** Asthma is currently being treated with a controller medication and the subject has been on a controller medication for the past 12 weeks. Subjects will be expected to continue controller therapy for the duration of the study.
4. **Male or Eligible Female Subjects:**

A female is eligible to enter and participate in the study if she is of:

Non-child bearing potential (i.e., physiologically incapable of becoming pregnant, including any female who is post-menopausal or surgically sterile). Surgically sterile females are defined as those with a documented hysterectomy and/or bilateral oophorectomy or tubal ligation. Post-menopausal females are defined as being amenorrhoeic for greater than 1 year with an appropriate clinical profile, e.g., age appropriate, > 45 years, in the absence of hormone replacement therapy.

OR

Child bearing potential, has a negative pregnancy test at screening, and agrees to acceptable contraceptive methods approved in their local country, when used consistently and correctly (i.e., in accordance with the approved product label and the instructions of the physician) for the duration of the study and for 4 months after the last study drug administration (see [Appendix 5](#)).

A urine pregnancy test is required of all females of child-bearing potential at each scheduled study visit prior to the injection of study treatment, and at the Exit Visit, EW or Discontinuation of IP Visit.

5. **French subjects:** In France, a subject will be eligible for inclusion in this study only if either affiliated to or a beneficiary of a social security category.

6.2. Exclusion Criteria

A subject will not be eligible for inclusion in this study if ANY of the following criteria apply:

1. **MEA115666 or 201312 IP Discontinuation:** Subjects withdrawn from IP or withdrawn from study participation from either MEA115666 or 201312 for safety reasons
2. **Health Status:** Clinically significant deterioration in health status at the completion of participation or EW from either the MEA115666 or 201312 trials which in the opinion of the investigator would make the subject unsuitable for participation in this study.
3. **Pregnancy:** Subjects who are pregnant or breastfeeding. Subjects should not be enrolled if they plan to become pregnant during the time of study participation.
4. **Cardiovascular:** Subjects who have severe or clinically significant cardiovascular disease uncontrolled with standard treatment. Including but not limited to:
 - known ejection fraction of <30% OR
 - severe heart failure meeting New York Heart Association Class IV classification OR
 - hospitalised in the 12 months prior to Visit 1 for severe heart failure meeting New York Heart Association Class III OR
 - angina diagnosed less than 3 months prior to Visit 1 or at Visit 1
5. **12-Lead ECG:** ECG which has a clinically significant abnormality observed at the Screening Visit as determined by the investigator. Subjects with the following abnormalities are excluded from study participation:
 - QTcF > 450 msec, or
 - QTcF >480 msec for subjects with Bundle Branch Block.
6. **Malignancy:** A current malignancy or previous history of cancer in remission for less than 12 months prior to screening (Subjects that had localized carcinoma of the skin which was resected for cure will not be excluded). [**Note for South Korea:** Korean subjects with a diagnosis of malignancy within 5 years are excluded].
7. **Other Monoclonal Antibodies:** Subjects who have received any monoclonal antibody within 5 half-lives of Visit 1.
8. **Adherence:** Subjects who have known evidence of lack of adherence within studies MEA115666 or 201312 (less than 80%) to controller medications, scheduled study visits and/or ability to follow physician's recommendations.
9. **Smoking status:** Current smokers

10. **Inability to read:** In the opinion of the Investigator, any subject who is unable to read and/or would not be able to complete a questionnaire.

6.3. Randomization Criteria

6.3.1. Randomization Inclusion Criteria

Subjects are eligible for randomization if ALL of the following are met:

1. **Continuous Mepolizumab Treatment:** Documented evidence of at least **3 years (156 weeks) of treatment with mepolizumab** with no treatment gaps of more than 12 weeks (84 days) between any two doses while treated with mepolizumab. See Section 5.1 for the definition of continuous mepolizumab treatment.
2. **eDiary Compliance:** Compliance with completion of the eDiary defined as:
 - Symptom Scores:** Completion of **symptom scores** on 4 or more days out of the last 7 days immediately preceding Visit C1.
 - Rescue Medication Use:** Completion of information relating to **rescue medication use** on 4 or more days out of the last 7 days immediately preceding Visit C1.
 - PEF Measurements:** Completion of **PEF measurements** on 4 or more days out of the last 7 days immediately preceding Visit C1.
 - Night time awakenings requiring rescue medication:** Completion of **night time awakenings** on 4 or more days out of the last 7 days immediately preceding Visit C1.

Subjects who fail this criterion in the run-in Part B may extend their run-in Part B by 4 weeks, and be re-educated on the importance of completion of eDiary daily entries.

3. **Maintenance Asthma Therapy:** No changes in the dose or regimen of baseline ICS and/or additional controller medication (except for OCS for the treatment of an exacerbation) during the fixed run-in period (Part B).

6.3.2. Randomization Exclusion Criteria

Subjects should not be randomized if ANY of the following are met:

1. **Health Status:** Clinically significant deterioration in health status during Part A or Part B which in the opinion of the investigator would make the subject unsuitable for participation in this study.
2. **12-Lead ECG as assessed at Visit B1:** ECG which has a clinically significant abnormality as assessed at Visit B1, as determined by the investigator. Subjects with the following abnormalities are excluded from further study participation:
 - QTcF > 450 msec, or

- QTcF >480 msec for subjects with Bundle Branch Block.

3. Liver function as assessed at Visit B1:

Alanine transaminase (ALT) >2x upper limit of normal (ULN); and

Bilirubin >1.5xULN (isolated bilirubin >1.5xULN is acceptable if bilirubin is fractionated and direct bilirubin <35%)

Current active liver or biliary disease (with the exception of Gilbert's syndrome or asymptomatic gallstones or otherwise stable chronic liver disease per investigator assessment).

NOTES:

- Stable chronic liver disease should generally be defined by the absence of ascites, encephalopathy, coagulopathy, hypoalbuminaemia, oesophageal or gastric varices, or persistent jaundice, or cirrhosis.
 - Chronic stable hepatitis B and C (e.g., presence of hepatitis B surface antigen (HBsAg) or positive hepatitis C antibody test result at screening or within 3 months prior to first dose of study treatment) are acceptable if subject otherwise meets entry criteria
4. **Pregnancy:** Positive pregnancy test
 5. **Immunogenicity:** Positive neutralizing antibody status based on the last result obtained.
 6. **Smoking status:** Current smokers
 7. **Current Asthma Exacerbation:** Subjects with an asthma exacerbation (or asthma worsening) that has not resolved completely within 7 days of Visit C1. Subjects who experience an exacerbation (or asthma worsening) in the fixed run-in Part B which is not resolved within 7 days of Visit C1 may extend their run-in Part B by 4 weeks.

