6.5. Study Withdrawal Prior to Randomization: Withdrawal during Part A or Part B

Subjects have the right to discontinue study participation before the end of the study. A subject may also be asked to discontinue study participation at the investigator's discretion or because the subject met the protocol defined stopping criteria detailed below.

Subjects in Parts A or B of the study **MUST** discontinue study participation if any of the following stopping criteria are met:

1. **Liver Chemistry:** Meets any of the protocol-defined liver chemistry stopping criteria (see [Appendix 2](#)).

Liver chemistry stopping and increased monitoring criteria have been designed to assure subject safety and evaluate liver event etiology (in alignment with the FDA premarketing clinical liver safety guidance).

<http://www.fda.gov/downloads/Drugs/GuidanceComplianceRegulatoryInformation/Guidances/UCM174090.pdf>

If the liver chemistry stopping criteria are met by any subject participating in this study, treatment restart or re-challenge is not permitted.

2. **Pregnancy:** Positive pregnancy test
3. **Laboratory abnormality:** Evidence of clinically significant abnormality in the haematological or biochemical screen, which in the opinion of the investigator would make the subject unsuitable for participation in this study.
4. **Hepatitis Status:** Positive Hepatitis B Surface Antigen (HBsAg) screen conducted at Visit 1.
5. **ECG:** Discontinuation is required if any of the following ECG criteria are met during the study:
 - QTcF>500 msec or uncorrected QT>600 msec
 - Change from Visit 1 baseline: QTcF> 60msec

For patients with underlying **bundle branch block**, follow the discontinuation criteria listed below:

Visit 1 Baseline QTc with Bundle Branch Block	Discontinuation QTc with Bundle Branch Block
< 450 msec	> 500 msec
450 – 480 msec	≥ 530 msec [Note: QTc(F)>500 msec for Korean subjects]

Details on performing ECG assessments can be found in Section 8.4.5.

Subjects who discontinue open-label mepolizumab/withdraw from study participation during Part A or Part B should return to the clinic for an Early Withdrawal (EW) visit (Section 6.6.1) and to return any study materials approximately 4 weeks following their last dose of open-label mepolizumab. No additional follow-up is needed.

Subjects withdrawing from study participation in Part A or Part B, prior to randomization will be classified as **run-in failures**, as appropriate (Section 6.4).

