13.3. Appendix 3: Liver Safety Required Actions and Follow up Assessments

Phase III-IV liver chemistry stopping and increased monitoring criteria have been designed to assure subject safety and evaluate liver event etiology (in alignment with the FDA premarketing clinical liver safety guidance).

<http://www.fda.gov/downloads/Drugs/GuidanceComplianceRegulatoryInformation/Guidances/UCM174090.pdf>

Phase III-IV liver chemistry stopping criteria and required follow up assessments

Liver Chemistry Stopping Criteria - Liver Stopping Event	
ALT-absolute	ALT \geq 8xULN
ALT Increase	ALT \geq 5xULN but <8xULN persists for \geq 2 weeks ALT \geq 3xULN but <5xULN persists for \geq 4 weeks
Bilirubin^{1,2}	ALT \geq 3xULN and bilirubin \geq 2xULN (>35% direct bilirubin)
INR²	ALT \geq 3xULN and INR>1.5, if INR measured
Cannot Monitor	ALT \geq 5xULN but <8xULN and cannot be monitored weekly for \geq 2 weeks ALT \geq 3xULN but <5xULN and cannot be monitored weekly for \geq 4 weeks
Symptomatic³	ALT \geq 3xULN associated with symptoms (new or worsening) believed to be related to liver injury or hypersensitivity
Required Actions and Follow up Assessments following ANY Liver Stopping Event	
Actions	Follow Up Assessments

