
ALT \geq5xULN and $<$8xULN and bilirubin $<$2xULN without symptoms believed to be related to liver injury or hypersensitivity, and who can be monitored weekly for 2 weeks.
 
OR
 
ALT \geq3xULN and $<$5xULN and bilirubin $<$2xULN without symptoms believed to be related to liver injury or hypersensitivity, and who can be monitored weekly for 4 weeks.
	
 • Notify the GSK medical monitor within 24 hours of learning of the abnormality to discuss subject safety. • Subject can continue study treatment • Subject must return weekly for repeat liver chemistries (ALT, AST, alkaline phosphatase, bilirubin) until they resolve, stabilise or return to within baseline • If at any time subject meets the liver chemistry stopping criteria, proceed as described above • If ALT decreases from ALT \geq5xULN and $<$8xULN to \geq3xULN but $<$5xULN, continue to monitor liver chemistries weekly. • If, after 4 weeks of monitoring, ALT $<$3xULN and bilirubin $<$2xULN, monitor subjects twice monthly until liver chemistries normalize or return to within baseline.

13.4. Appendix 4: Definition of and Procedures for Recording, Evaluating, Follow-Up and Reporting of Adverse Events

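### Randomisation exclusion 3 joins its ALT and bilirubin limits with 'and', so read literally it excludes on laboratory values only when both are raised; it should say 'or'

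*Protocol*

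**What the plan says.** Section 6.3.2 of the protocol bars randomisation if any one of its numbered criteria is met. Criterion 3, assessed at Visit B1, has three items on separate lines:

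- an ALT limit, ending in a connector: "Alanine transaminase (ALT) >2x upper limit of normal (ULN); and";
- bilirubin above 1.5xULN, with a bracketed exemption: "isolated bilirubin >1.5xULN is acceptable if bilirubin is fractionated and direct bilirubin <35" per cent;
- current active liver or biliary disease, with listed exceptions and no connector before it.

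Criterion 2 in the same list, on the ECG, joins its alternatives with 'or': "QTcF > 450 msec, or" a higher limit for bundle branch block.

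The introduction to section 6 allows no deviations from the criteria and adds that "adherence to the criteria as specified in the protocol is essential".

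**The concern.** The connector decides whether each laboratory limit excludes alone or only in combination. With 'and', a subject with a high ALT and normal bilirubin does not meet the laboratory part, however high the ALT, and neither does a subject with a high bilirubin and normal ALT, whatever the direct fraction.

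The exemption points the other way. An isolated bilirubin elevation needs excusing only if bilirubin alone would otherwise exclude. The criterion therefore contradicts itself, and section 6 tells sites to apply it as printed.

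At stake are a safety threshold and consistent eligibility across sites. If sites read the criterion differently, the same Visit B1 result could be a run-in failure at one site and eligible at another. The SAP's summary of randomisation-criteria deviations (section 4.1) is based on what sites record on the eCRF, and Tables 1.15 and 1.16 report failed randomisation criteria, so these displays would carry the inconsistency.

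**Working it through.** No sample size, power or alpha figure is involved. The check is one of logic, followed by a comparison with the protocol's other liver rules.

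**Step 1: does the exemption do anything?** Let A be ALT above 2xULN, B be bilirubin above 1.5xULN, and E be bilirubin fractionated with direct below 35%. E matters only when B is true, which leaves six combinations. 'Isolated' is taken to mean B without A, so the exemption applies when B and E hold and A does not. The rules compared are:

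- 'and': exclude if A and (B and not exempt)
- 'or': exclude if A or (B and not exempt)

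| A | B | E | 'and', no exemption | 'and', exemption | 'or', no exemption | 'or', exemption |
|---|---|---|---|---|---|---|
| no | no | no | admit | admit | admit | admit |
| no | yes | no | admit | admit | exclude | exclude |
| no | yes | yes | admit | admit | exclude | admit |
| yes | no | no | admit | admit | exclude | exclude |
| yes | yes | no | exclude | exclude | exclude | exclude |
| yes | yes | yes | exclude | exclude | exclude | exclude |

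The exemption changes 0 of 6 rows under 'and' and 1 of 6 under 'or'. Only 'or' gives every clause a function.

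**Step 2: which admitted patterns are caught elsewhere?** Section 6.5, item 1, requires discontinuation in Parts A and B if a subject "Meets any of the protocol-defined liver chemistry stopping criteria". Appendix 3 lists six stopping rows and two increased-monitoring criteria, and every one needs ALT of at least 3xULN. The lowest stopping band based on ALT alone is "3xULN but <5xULN persists for" at least 4 weeks. Under monitoring, "Subject must return weekly for repeat liver chemistries (ALT, AST, alkaline phosphatase, bilirubin) until they resolve, stabilise or return to within baseline".

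| Visit B1 pattern | Literal 'and' | 'or' | Numeric liver rule elsewhere |
|---|---|---|---|
| ALT 2.5xULN, bilirubin normal | admit | exclude | none |
| ALT 4xULN, bilirubin normal, no symptoms | admit | exclude | weekly tests; stop if it lasts 4 weeks or cannot be monitored |
| ALT 6xULN, bilirubin normal, no symptoms | admit | exclude | weekly tests; stop if it lasts 2 weeks or cannot be monitored |
| ALT 8xULN, bilirubin normal | admit | exclude | immediate stop |
| Bilirubin 1.8xULN, direct 20%, ALT normal | admit | admit (exempt) | none |
| Bilirubin 1.8xULN, direct 40% or not fractionated, ALT normal | admit | exclude | none |
| ALT 2.5xULN and bilirubin 1.8xULN | exclude | exclude | none |

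The bands that the literal rule admits and the 'or' rule excludes, and that no stopping rule closes at once, are:

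1. isolated ALT above 2 and below 3xULN, with no other numeric rule (the symptomatic stopping row also starts at 3xULN);
2. isolated, symptom-free ALT from 3 to below 8xULN that is transient: monitored weekly, but stopped only if it persists or cannot be monitored;
3. isolated bilirubin above 1.5xULN with direct 35% or more, or not fractionated, with no other numeric rule.

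**Step 3: is it corrected anywhere?** No other section of the protocol or SAP restates the criterion with 'or'. Amendments 1 and 2 changed other items in the same list (nos. 5 and 7) and left no. 3 alone.

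**Step 4: does it reach the analysis?** None of the eight Per Protocol exclusions in SAP section 11.1.1 concerns liver function, and the sample size and the primary Cox analysis do not depend on the criterion.

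**The case against.** The strongest reply is that the connector is only a list separator. The list opens with a statement that any item suffices, the items sit on separate lines, and the third has no connector. On that reading each limit excludes alone, the exemption works, and a careful site would reach the right answer. This shows that the intent can be recovered, but it does not rescue the text. The opening statement governs the numbered criteria and does not say how the parts within no. 3 combine. The separator reading also leads to the same correction.

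The second reply is that other safeguards cover the gap. Section 6.5, item 3, requires discontinuation in Parts A and B for "Evidence of clinically significant abnormality in the haematological or biochemical screen, which in the opinion of the investigator" makes the subject unsuitable. Section 6.3.2 separately excludes for deterioration in health and for active liver disease. Section 8.4.6 requires clinically significant abnormal results to be repeated, and chemistry is tested again at C1, Week 24 and Week 52. All of this stands and is why the impact is low. But these safeguards turn on the investigator's judgement and do not supply the numeric limit that criterion 3 was written to set.

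Third, subjects have already had at least 3 years of mepolizumab, half are then assigned placebo, and the protocol's risk table lists no hepatic risk. That also stands, and it limits the likely harm. Finally, the eCRF pages and the Study Reference Manual are not available, so how sites were shown the criterion is unknown. No claim that subjects were wrongly randomised can be made.

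**Conclusion.** The concern holds. As printed, the laboratory part of criterion 3 needs both ALT and bilirubin to be raised, which leaves its own exemption without effect; 'or' is the only connector consistent with the rest of the criterion. This is a drafting slip in an operative safety limit.

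Its practical weight is low. Bands 1 and 3 above are left to investigator judgement alone, and band 2 is under weekly monitoring. The number of subjects in these bands cannot be derived from the documents. Statistical inference is unaffected. The conclusion rests on reading 'and' as a logical connector and 'isolated' bilirubin as bilirubin raised without ALT above 2xULN.

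**What to change.** In section 6.3.2, criterion 3, replace 'and' with 'or' after the ALT limit, and insert 'or' before the item on current active liver or biliary disease, so that each of the three items excludes alone. Leave the isolated-bilirubin exemption as it is. The cost is two connector words in the protocol, with no new test, visit or analysis.
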